## 7. CLINICAL EVALUATIONS AND PROCEDURES

### 7.1 Schedule of Events

Study Events	Consenting/ Screening	Baseline/ Randomization	Intervention (12 month (52 ± 4 wks))								
			Months 1 - 3	Month 3 Visit (13 ± 2 wks)	Months 4 - 6	Month 6 Visit (26 ± 4 wks)	Months 7 - 9	Month 9 Visit (39 ± 2 wks)	Months 10 - 12	Month 12 Visit (52 ± 4 wks)	Follow up
Consent, med records release form	X										
Medical history, performance status	X										
anthropometric measurements	X	X				X				X	
Vital signs (Temp, BP, Pulse)	X	X		X		X		X		X	
Concomitant meds	X	X		X		X		X		X	
Breast cancer risk assessment	X										
Menstrual pattern/cycle review	X	X		X		X		X		X	
Menstrual cycle diary	X	X	X	X	X	X	X	X	X	X	
Fasting blood (CBC/Diff, CMP, lipids, FSH  , estradiol  )	X									X	
Fasting blood for research endpoints		X				X				X	
Urine pregnancy test	X	X		X		X		X		X	
Urine for research endpoints		X				X				X	
AFFQ, AAFQ		X								X	
NAF collection		X				X				X	
Breast MRI 		X				X				X	
Core biopsy, if consented		X				X					
Final eligibility assessment		X									
Randomization		X									
Dispense study agent		X				X					
Intake calendar			X	X	X	X	X	X	X	X	
Adverse events diary		X	X	X	X	X	X	X	X	X	X
Adverse events review		X		X		X		X		X	X
Return study agent						X				X	
Compliance assessment				X		X		X		X	
Case report form completion	X	X		X		X		X		X	X
Telephone/email contact 			X		X		X		X		

 Study personnel will contact subjects within a week after study agent has been initiated and within a week following scheduled dose increase to assess compliance and any potential problems. Additional periodic telephone or email contact will occur between study visits and as needed to review study procedures, adverse events, concomitant medications, and to address any subject concerns.

 FSH (follicle-stimulating hormone) and/or estradiol at screening for women with uncertain menopausal status.

 Women who cannot fit into the MRI scanner due to the large body size will continue the study and undergo all other study procedures.

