## 9. STATISTICAL CONSIDERATIONS

### 9.1 Analysis Plan

The primary study endpoint is to compare the change in breast density as measured by FWR-MRI (when measured at baseline, 6 and 12 months) between metformin and placebo groups. Additional endpoints such as systemic hormone and cytokines, body weight, waist circumference, and waist-hip ratio will be measured at baseline, 6 and 12 months. Analysis for all study endpoints will be based on a linear mixed-effects model for the observed values across time, to adjust for the correlation among measurements within the same woman. The main effects in the model will be time (0, 6, 12), treatment group (metformin versus placebo), and the interaction between time and treatment group. The time parameter tests if there is a change among placebo treated women, while the group-by-time interaction tests if the change in metformin treated women differs from that in the placebo group. We expect that a simpler covariance structure, such as compound symmetry, will be adequate for repeated measurements within the same woman (since the measurements are equally spaced). Alternatively, we will compare correlation structures for the longitudinal measurements using Akaike's information criterion. All endpoints will be first assessed for normality, and transformations (such as a logarithmic transformation) will be used as necessary to reduce skewness prior to statistical analysis.

Secondary analyses will assess whether differences in the changes in FWR-MRI between the metformin and placebo groups remain after adjustment for potential explanatory variables, such as changes in body weight, systemic hormones, and cytokines. These explanatory variables will be added as independent predictors in the linear mixed-effects models. These analyses will be restricted to explanatory variables that have demonstrated statistically significant metformin effects across time.

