### **9.2 Sample Size Justification**

Our sample size ensures adequate power to test all primary specific aims. We assume an initial sample size of 75 women per arm and allow the possibility of up to 20% dropout for the 12-month follow-up measurement. This results in at least 60 evaluable women per group. To justify the sample size, we use the simplified comparison of change between 12 months versus baseline (ignoring the 6 month measurement). For the FWR-MRI-derived change in breast density, we will be able to detect a decrease of 0.516 standard deviation (SD) units in the metformin treated women with 80% statistical power, assuming a two-sided  $\alpha$  of 0.05. To estimate what this change would be in relation to breast density, we used the relationship between breast density and  $\log(\text{Fra50})$  based on our previous data. Based on an analysis of our cross-sectional data, the estimated SD of  $\log(\text{Fra50})$  is 2.40. Thus, a decrease of 0.516 SD units corresponds to a change of  $-1.2384$  ( $-0.516 \times 2.40$ ). Based on the regression line, this is equivalent to a 10% decrease in breast density as determined by standard mammography. For the additional primary outcomes (such as systemic hormones, cytokines, and weight), we will be able to detect a difference of 0.516 SD units with 80% statistical power, assuming a sample size of 60 evaluable women per group. Based on our previous experience, we anticipate that 65% of the proposed cohort will provide sufficient NAF for metabolomic analysis, which results in 39 women per group (allowing for up to 20% drop-out). This will allow us to detect a difference of 0.643 SD units with 80% statistical power.

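### Equal visit spacing does not justify compound symmetry, the AIC comparison is not binding, and the group-by-time test leaves its time coding, degrees of freedom and month open

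*Combined protocol and SAP*

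**What the plan says.** Section 9.1 (Analysis Plan) analyses every endpoint with a linear mixed-effects model containing time (0, 6, 12), group and their interaction. On the within-woman covariance it expects that "a simpler covariance structure, such as compound symmetry, will be adequate for repeated measurements within the same woman (since the measurements are equally spaced", so equal spacing of the visits is the reason given. The next sentence reads: "Alternatively, we will compare correlation structures for the longitudinal measurements using Akaike's information criterion". It states neither when that comparison is made nor which structures enter it, and it does not mention robust standard errors.

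The treatment effect is tested through the interaction: "the group-by-time interaction tests if the change in metformin treated women differs from that in the placebo group". The section does not say whether time is categorical or linear, how many degrees of freedom the test has, or which month it concerns.

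Section 9.2 (Sample Size Justification) works from a single contrast: "we use the simplified comparison of change between 12 months versus baseline (ignoring the 6 month measurement". It calls this a simplification and does not declare it the primary analysis. The only variability figure is an SD of 2.40 for log(Fra50), introduced by "Based on an analysis of our cross-sectional data, the estimated SD of". No SD of change and no within-woman correlation is given.

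**The concern.** Compound symmetry makes two claims: the variance is the same at all three visits, and measurements 12 months apart are as strongly correlated as measurements 6 months apart. Equal spacing implies neither. Spacing would be relevant to a structure in which correlation is a function of lag, but compound symmetry says that lag does not matter. A cross-sectional SD cannot inform either claim.

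With three visits, the compound-symmetry model estimates one common variance for all pairwise changes. If the true variance of the 0-to-12 change is larger than the average of the three pairwise variances, the model's standard error for the month-12 contrast is too small, so the p-value and interval are too optimistic. If it is smaller than the average, the test is conservative and loses power. Whether this affects the primary result depends on the form of the interaction test, which the plan leaves open. The same model serves the hormone, cytokine and anthropometric endpoints.

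**Working it through.** **Inputs from the documents (9.1, 9.2).** Two-sided α 0.05; 75 randomised per arm; up to 20% dropout, so 75 × 0.8 = 60 evaluable per arm; detectable difference 0.516 SD with 80% power; visits at 0, 6 and 12 months.

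**Assumed, because the documents give no values.** All correlations (written as 6-month/12-month) and all visit variances (months 0, 6, 12).

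**Step 1: the plan's own figure.** A two-sample t-test with 60 per arm (118 df) has 80% power at 0.5157 SD, and power 80.0% at 0.516 SD. The figure in 9.2 reproduces, as a 1-df test of the month-12 change. The normal approximation used below gives Φ(0.516 × √30 − 1.96) = 80.7%.

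**Step 2: formula.** Let d(i,j) = Var(Yi − Yj). With a saturated time-by-group mean and complete data, compound symmetry takes the variance of the month-12 change to be the mean of d(0,6), d(6,12) and d(0,12). The true value is d(0,12). So:

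- SE ratio (model/true) R = √[mean d / d(0,12)]
- type I error = 2Φ(−1.96 R)
- power at the sized effect = Φ(0.516√30 − 1.96 R)

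Example, 0.80/0.75 with equal variances: d = 0.40, 0.40, 0.50; mean 0.433; R = √(0.433/0.50) = 0.931; error = 2Φ(−1.825) = 6.8%.

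**Step 3: results for the 1-df month-12 test, compound symmetry kept, model-based SE, 60 per arm.**

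| Correlations | Variances | R | Type I error |
|---|---|---|---|
| 0.80/0.80 | equal | 1.000 | 5.0% |
| 0.80/0.79 | equal | 0.984 | 5.4% |
| 0.50/0.45 | equal | 0.969 | 5.7% |
| 0.70/0.65 | equal | 0.951 | 6.2% |
| 0.80/0.75 | equal | 0.931 | 6.8% |
| 0.90/0.85 | equal | 0.882 | 8.4% |
| 0.50/0.25, AR(1) | equal | 0.882 | 8.4% |
| 0.80/0.64, AR(1) | equal | 0.839 | 10.0% |
| 0.90/0.81, AR(1) | equal | 0.827 | 10.5% |
| 0.80/0.80 | 1, 1.25, 1 | 1.050 | 4.0% (power 78%) |
| 0.80/0.80 | 1, 1.5, 1 | 1.111 | 2.9% (power 74%) |
| 0.80/0.75 | 1, 1.25, 1 | 0.974 | 5.6% |
| 0.80/0.75 | 1, 1.5, 1 | 1.027 | 4.4% (power 79%) |
| 0.80/0.80 | 1, 1, 1.5 | 0.956 | 6.1% |

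Using the t critical value with 236 df instead of 1.96 lowers these error rates by about 0.1 to 0.2 points.

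**Step 4: simulation check.** REML fits, 60 per arm, complete data, 20,000 null trials per setting (Monte Carlo SE about 0.15–0.2 points). Compound symmetry rejected in 4.9% (0.80/0.80), 6.0% (0.70/0.65), 6.8% (0.80/0.75), 9.9% (0.80/0.64) and 3.2% (0.80/0.80 with variances 1, 1.5, 1). An unstructured covariance gave 4.7–5.5%. With about 20% dropout completely at random, two separate simulations of 4,000 trials per setting gave 6.6–7.3% (0.80/0.75), 9.5–9.7% (0.80/0.64) and 2.7–3.0% (month-6 variance 1.5, 0.80/0.80). Unstructured gave 5.3%, 4.9% and 5.0% in the same three settings.

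**Step 5: routes that avoid most of the error.** If AIC is run, error is 4.8–6.0% with complete data, depending on candidates and setting, and 4.9–6.2% with dropout. A joint 2-df interaction test under compound symmetry stays at about 4.7–5.8%.

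**Step 6: power of the 2-df test at the sized effect, if compound symmetry is true.** In units of the SD of change, the two treatment differences each have variance 2/60 and correlation 0.5, so the noncentrality is 40 × (δ6² − δ6δ12 + δ12²).

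- Effect linear in time (0.258, 0.516): 40 × 0.1997 = 7.99; power 71% on F(2, 236).
- Effect complete by month 6 (0.516, 0.516): 40 × 0.2663 = 10.65; power 84%.

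**The case against.** The plan does not commit itself to compound symmetry. It states an expectation and then says that structures will be compared by AIC, and the natural charitable reading is that some check will be made. If so, error is near 5–6%. If time is categorical and the interaction is tested jointly on 2 df, error is also near 5–6% whatever the structure. The inflated or deflated rates need three things together: compound symmetry kept, model-based standard errors, and a 1-df month-12 or slope test. All of this stands. It does not remove the point, because the AIC sentence is only an alternative with no trigger or candidates. An analyst who keeps compound symmetry unchecked follows the plan just as one who runs AIC does.

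The size is also open to dispute. A drop of 0.01 at a 6-month correlation of 0.80 moves error only to 5.4%. The conservative case needs a variance peak at month 6, which nothing in the documents suggests, and decay and a month-6 peak partly offset each other. With the planned dropout, simulated power was 80% at a month-6 variance of 1.25, equal to plan, and 74–79% at 1.5. These limits stand too.

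A reader might infer three stronger points that the documents do not support:

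- That the primary test will run at a particular inflated level. No within-woman covariance is given, so no single rate can be claimed.
- That no primary test is named. The group-by-time interaction is named; its coding, df and month are missing.
- That the visit windows in 7.1 (26 ± 4 and 52 ± 4 weeks) count against compound symmetry because gaps may be uneven. Compound symmetry does not depend on spacing, so the windows have no bearing here.

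**Conclusion.** The concern holds in a conditional form. The stated reason for compound symmetry is wrong, the documents offer no other support for it, and the plan's wording allows it to be kept without a check. Under the three conditions above, the actual size of a nominal 5% test ranges in the settings tried from about 3% (month-6 variance 1.5 times the others, equal correlations) to about 10% (AR(1) at 0.8–0.9). It is 5.4–8.4% where the 12-month correlation is 0.01–0.05 below the 6-month one. Every one of these figures rests on assumed covariances.

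The open form of the interaction test matters separately. A 2-df test protects the error rate but is not the test that 9.2 sized: its power at 0.516 SD is about 71% or 84%, depending on when the effect appears, if compound symmetry is true. This is a specification gap to close before analysis, not evidence that the design cannot answer its question.

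**What to change.** In 9.1:

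- Delete the equal-spacing rationale.
- Replace the compound-symmetry and AIC sentences with categorical time and an unstructured within-woman covariance, fitted by REML with Kenward-Roger degrees of freedom. Allow a simpler structure only if that model does not converge.
- Name the month-12 group-by-time contrast, the one sized in 9.2, as the single primary test.

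Making AIC mandatory with a listed set of candidates would also close the wording gap. It is the weaker choice, since under mild decay it leaves error at about 5–6%.

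The cost is wording, plus six covariance parameters instead of two. If compound symmetry is in fact true, power at 0.516 SD with complete data is 80.0% (118 df) instead of 80.4% (236 df).

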**Anthropometric Measures.** Studies suggested that weight reduction reduces risk of postmenopausal breast cancer. For example, in the Iowa Women’s Health Study, women who lost >5% of their body weight before menopause had 40% fewer breast cancers in the postmenopausal period compared with women who continued to gain weight (95). In addition to weight gain, body fat distribution has also been suggested to play a role in the risk of breast cancer. Positive association between central adiposity and breast cancer risk was observed in some studies (96-99). Studies have shown that metformin intervention resulted in weight reduction and decreased waist circumference in overweight or obese individuals without type 2 diabetes, although these trials were small and of weak design (reviewed by (14)).

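### Screening explanatory variables on same-trial significance drops real but modest mediators of the density effect and overstates the attenuation for modest ones that pass

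*Combined protocol and SAP*

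**What the plan says.** Section 9.1 (Analysis Plan) describes the explanatory analysis this way: "Secondary analyses will assess whether differences in the changes in FWR-MRI between the metformin and placebo groups remain after adjustment for potential explanatory variables". Its examples of candidates are weight change and changes in circulating hormones or cytokines. The variables are added as predictors to the linear mixed-effects model for density. Entry is then limited: "These analyses will be restricted to explanatory variables that have demonstrated statistically significant metformin effects across time".

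The test that decides entry appears to be the one Section 9.1 uses for every endpoint, where "the group-by-time interaction tests if the change in metformin treated women differs from that in the placebo group", with measurements at 0, 6 and 12 months. No significance level is given for this use of it.

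Section 9.2 (Sample Size Justification) starts from 75 women per arm and up to 20% dropout: "This results in at least 60 evaluable women per group". For hormones, cytokines and weight it states that "we will be able to detect a difference of 0.516 SD units with 80% statistical power". Neither section names variables that enter regardless of significance, gives an interval for the explained part, or corrects for the selection.

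**The concern.** The analysis asks whether the density effect runs through weight or hormones. Under the rule, a variable is considered only after winning a significance test in a trial whose stated power for it is 80% at about half an SD. Two consequences follow.

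First, a non-significant result is treated as if it showed no effect. Weight is the case that matters most. Section 2.3.1 defines the density measure as the fraction of breast voxels holding more water than fat, so a change in breast fat could itself move the endpoint. Section 2.3.2 reports weight and waist reductions with metformin, "although these trials were small and of weak design", so a modest effect cannot be excluded. If weight misses significance, the weight-adjusted density result is not produced. The IGF axis, which Section 2.2 gives as part of the reason to expect a density effect, faces the same screen.

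Second, a modest effect that passes does so partly because its estimate came out high. The fall in the density difference after adjustment then looks larger than it should.

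**Working it through.** **Inputs.** From Section 9.2: 60 evaluable women per arm, two-sided 0.05, detectable difference 0.516 SD. Assumed: the screen also uses two-sided 0.05; entry is approximated by a two-sample comparison of 12-month change, the simplification Section 9.2 itself uses; true marker effects range from 0.2 to 0.8 SD, because the documents give none.

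**1. The plan's figure.** The noncentral t with 118 degrees of freedom and noncentrality d × √(60/2) gives 80% power at d = 0.5157 SD. The stated 0.516 SD reproduces (power 80.0%).

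**2. Probability of entry.** This is the power of the same test at the true effect d. It equals 50% at d = 0.361 SD.

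**3. Size of an admitted estimate.** SE = √(2/60) = 0.183 SD. The smallest significant estimate is c = 1.96 × 0.183 = 0.358 SD. Ignoring the negligible opposite tail, the mean estimate given entry is d + SE × φ(z)/(1 − Φ(z)), with z = (c − d)/SE. At d = 0.3, z = 0.317 and the mean is 0.3 + 0.183 × 0.379/0.376 = 0.48 SD, or 1.6 times the truth.

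**4. Effect on attenuation.** Linear mediation simulation on change scores: 60 per arm, 40,000 trials, total density effect 0.516 SD, assumed marker-to-density slope b = 0.4, no marker–outcome confounding. The true indirect effect is d × b, and the true share is d × b/0.516. The estimated share is the mean indirect effect divided by the mean total effect, among trials in which the marker entered.

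| True effect (SD) | Enters | Left out | Admitted estimate ÷ truth | Indirect effect, true → admitted | Share, true → admitted |
|---|---|---|---|---|---|
| 0.2 | 19% | 81% | 2.3 | 0.080 → 0.181 | 16% → 29% |
| 0.3 | 37% | 63% | 1.6 | 0.120 → 0.194 | 23% → 33% |
| 0.4 | 58% | 42% | 1.3 | 0.160 → 0.208 | 31% → 37% |
| 0.516 | 80% | 20% | 1.12 | 0.206 → 0.232 | 40% → 43% |
| 0.8 | 99% | 1% | 1.00 | 0.320 → 0.322 | 62% → 62% |

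Without the screen, the mean indirect effect equals the truth in every row.

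**5. What is and is not biased.** At 0.3 SD, among admitted trials, the total density effect averages 0.591 against a true 0.516, and the adjusted difference averages 0.397 against a true 0.396. Selection depends only on the marker and the arm, and the adjusted model conditions on both, so the remaining difference is sound. The unadjusted difference is inflated in the selected trials, and so is the drop. Because the total rises as well, the share (0.194/0.591 = 33%) inflates less than the indirect effect (0.194/0.120 = 1.6 times).

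**6. Sensitivity.** With b = 0.3 the share at 0.3 SD goes from 17% to 25%; with b = 0.5, from 29% to 40%. If the 6-month visit is used under compound symmetry (correlation between the two changes 0.5), entry probability is 29% to 48% at 0.3 SD and 72% to 90% at 0.516 SD, depending on how the interaction is tested and when the effect appears.

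**The case against.** Asking for a demonstrated treatment effect before calling a variable explanatory is a recognisable choice, and this is a secondary analysis in a Phase II trial. The plan reports whether the difference remains after adjustment, not a mediated share, and step 5 shows that the remaining difference is unbiased for an admitted variable. All of this stands, and it limits the severity. It does not cover the variables left out, for which no adjusted result exists, and readers will set the adjusted estimate beside the unadjusted one.

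Three stronger readings are tempting and should be resisted.

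- A reader might infer that weight will usually be left out. That needs a true effect below about 0.36 SD. The documents give no such figure, and at the one effect size the plan states for these variables entry is 80%.
- A reader might infer that weight goes unexamined. It does not: weight, waist circumference and waist-hip ratio are endpoints with their own mixed models under Section 9.1. Only their entry into the density model is conditional.
- A reader might infer that every admitted variable has its role exaggerated. The overstatement is large at 0.2 to 0.3 SD, small at 0.516 SD and absent at 0.8 SD.

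**Conclusion.** The concern holds in conditional form. The rule selects on significance in the same women. It omits a real mediator more often than not if its effect is below about 0.36 SD, and one in five at the plan's own 0.516 SD. For modest effects that pass, it overstates the apparent attenuation by an amount that fades as the effect grows.

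These sizes rest on a two-sided 0.05 screen, 60 women per arm with both marker and density measured, a two-point approximation to the mixed model, and assumed slopes of 0.3 to 0.5. The true marker effects are unknown, so the documents do not show which row of the table applies. The primary comparison is unaffected. Severity is low to moderate: the planned analysis cannot reliably answer its own question for modest mediators, and the remedy is cheap.

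**What to change.** Delete the significance restriction in Section 9.1. Before unblinding, fix a short list drawn from the protocol's own rationale: change in weight, insulin, IGF-BP1, the IGF-1/IGF-BP3 ratio, testosterone, SHBG, leptin and adiponectin, as far as each is assayed. IGF-BP1 belongs on the list because Section 2.3.2 reports that metformin raises it while leaving IGF-1 unchanged.

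Fit the adjusted density model for each listed variable whatever its p-value. Report the adjusted difference and the indirect effect with a bootstrap confidence interval, labelled as explanatory.

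The cost is a wording change and a few more model fits. The downside is that some indirect effects will be near zero with wide intervals.

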**Secondary Endpoints:**

- Modulation of systemic hormones, growth factors, and cytokines (insulin, sex steroid hormone, IGF-axis, adipokines) and anthropometric measures
- Modulation of metabolomic profiles in NAF and plasma and correlations of metabolomic profiles with markers of breast cancer risk

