#### Research biomarkers

Fasting blood samples will also be collected during baseline, month 6 and at the end of intervention for research biomarker analyses. Approximately 30 ml of fasting blood will be drawn into two 10 ml SST or tiger top Vacutainer tubes and one 10 ml heparin Vacutainer tube. The blood in the SST or tiger top tubes will be allowed to clot for approximately 30 minutes at room temperature then centrifuged for serum separation. The heparin tube will be gently inverted to mix for anticoagulation. Serum from the SST tubes will be aliquoted into 10 x 1-2 ml cryovials and plasma from the heparin tube will be aliquoted into 5 x 1-2 ml cryovials. Samples will be labeled with the study ID, subject ID, and date of collection and stored at -80°C until analyses.

NAF will be collected at baseline, month 6 and at the end of intervention. NAF will be collected in small capillary tubes. The capillary tubes will then be stored in a 5 ml cryotube. Cryotubes will be labeled with the study ID, subject ID, and date of collection and stored at -80°C until analyses.

Clean catch urine will be collected at baseline, month 6 and at the end of intervention. Urine will be aliquoted into 4 x 1-2 ml cryovials. Cryovials will be labeled with the study ID, subject ID, and date of collection and stored at -80°C until analyses.

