For the metabolomic aim, pre- to post-intervention changes in all detectable compounds of known identity (currently comprising 397 biochemicals using the standard platforms offered by Metabolon, Inc) will be determined and compared between treatment groups using a two-sample t-test. An estimate of the false discovery rate ( $q$ -value) will be calculated (115) to take into account the multiple comparisons that normally occur in metabolomic-based studies. A low  $q$ -value ( $q \leq 0.10$ ) is an indication of high confidence in a result. While a higher  $q$ -value indicates diminished confidence, it does not necessarily rule out the significance of a result. Other lines of evidence may be taken into consideration when determining whether a result merits further scrutiny. Such evidence may include a) significance in another dimension of the study, b) inclusion in a common pathway with a highly significant compound, or c) residing in a similar functional biochemical family with other significant compounds.

Exploratory analyses will assess whether the observed metformin-induced changes in metabolite features are correlated with changes in FWR-MRI, body weight/composition, systemic hormones, and cytokines. The correlation will be estimated using a Pearson correlation coefficient. It is expected that any changes in these variables in the placebo group will reflect random variation only. Thus, these analyses will be restricted to the metformin group to overcome dilution of the potential correlations by individuals in the placebo group.

Exploratory analyses also will explore the correlation between baseline metabolite features and FWR-MRI, systemic hormones, and cytokines. These analyses will be restricted to

the metabolite features that are members of a common pathway to reduce the potential for an inflated alpha level.

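### The metabolite comparison uses a t-test on change with no adjustment for baseline; an ANCOVA on the same samples would be more precise at no cost in data

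*Combined protocol and SAP*

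**What the plan says.** Section 9.1 sets a general rule: "Analysis for all study endpoints will be based on a linear mixed-effects model for the observed values across time". It then defines the terms: "The main effects in the model will be time (0, 6, 12), treatment group (metformin versus placebo), and the interaction between time and treatment group". Baseline is therefore one of the modelled outcomes, not a covariate. The section also covers scale: "All endpoints will be first assessed for normality, and transformations (such as a logarithmic transformation) will be used as necessary to reduce skewness".

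The metabolomic aim then gets its own method in the same section. Changes in all detectable compounds of known identity (currently 397) "will be determined and compared between treatment groups using a two-sample t-test", followed by q-values with 0.10 as the mark of high confidence. No baseline covariate is named, and the plan does not call this an exception to the general rule. The schema lists as a secondary endpoint: "Modulation of metabolomic profiles in NAF and plasma and correlations of metabolomic profiles with markers of breast cancer risk".

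On sampling, section 8.1 states "NAF will be collected at baseline, month 6 and at the end of intervention" and, for blood, "Fasting blood samples will also be collected during baseline, month 6 and at the end of intervention for research biomarker analyses". Section 3 links NAF to metabolomics at baseline and at the end of intervention. At month 6 it describes the NAF and blood only as being for research biomarkers.

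Section 9.2 expects 65% of women to give enough NAF. That leaves 39 per group after dropout and a detectable difference of 0.643 SD with 80% power.

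**The concern.** In a randomised comparison, a t-test on change forces the slope of follow-up on baseline to be 1. If the true slope is lower, as it is with equal variances whenever r is below 1, the change score carries baseline noise that an adjusted analysis removes. The baseline value is already measured, so this precision is available without further sampling.

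The stakes are power in a screen of 397 compounds. The 80% in section 9.2 is for a single test at two-sided 0.05. A q-value rule over hundreds of compounds will usually work at a stricter p-value, where power is lower and added precision is worth more. For NAF, the sample is also smaller than the 60 per group assumed for the other outcomes.

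**Working it through.** **Inputs.** From section 9.2: 75 women per arm, up to 20% dropout, 65% NAF yield, two-sided alpha 0.05, 80% power, 0.643 SD for NAF, and 0.516 SD for outcomes with 60 per group. Assumed: r, the baseline-to-month-12 correlation of a metabolite (on the analysis scale), taken from 0.3 to 0.9; and equal variances at the two visits. I take post-intervention to mean month 12, as the sample size calculation does.

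**The plan's own figures.** 75 × 0.80 = 60 and 60 × 0.65 = 39. The noncentral t distribution gives a detectable difference of 0.6426 SD at n = 39 (stated 0.643) and 0.5157 SD at n = 60 (stated 0.516). Both reproduce.

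**Variance of the arm contrast**, with n per group and variance σ² at each visit:

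- change score: 4σ²(1 − r)/n
- ANCOVA: 2σ²(1 − r²)/n
- ratio, ANCOVA to change score: (1 + r)/2

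The detectable difference scales with the square root of the ratio. The relative number of women that the change score needs for equal precision is 2/(1 + r).

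| r | Variance ratio | Square root | NAF: 0.643 becomes | Extra women for change score | Power at 0.643, alpha 0.05 |
|---|---|---|---|---|---|
| 0.3 | 0.65 | 0.806 | 0.518 | 54% | 94% |
| 0.5 | 0.75 | 0.866 | 0.557 | 33% | 90% |
| 0.7 | 0.85 | 0.922 | 0.593 | 18% | 86% |
| 0.9 | 0.95 | 0.975 | 0.627 | 5% | 82% |

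Differences are in units of the SD of change. The change-score power is 80%, and the power figures come from the noncentral t. At an illustrative stricter threshold of 0.005, power is 48% for the change score and 73%, 65%, 58% and 51% for ANCOVA at the four values of r.

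**Plasma.** The NAF yield limit does not apply. If 60 per group are available, 0.516 becomes 0.416, 0.447, 0.476 and 0.503 by the same factors.

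**Unequal variances.** With SDs σ0 at baseline and σ1 at month 12, the change-score variance exceeds the ANCOVA variance by 2(σ0 − rσ1)²/n. This is never negative, and is zero only when the true slope rσ1/σ0 equals 1. ANCOVA costs one degree of freedom (75 instead of 76 for NAF).

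**Would the general mixed model do better?** With complete data, its month 12 group-by-time contrast has exactly the variance of the t-test on change: ratio 1.00 at every r tried, under compound symmetry and under AR(1). For dropout, 75 × 0.65 is about 49 NAF producers per arm. If 10 of them are lost after month 6, the ratio is 0.92 to 0.95 under compound symmetry and about 0.90 under AR(1). Under compound symmetry, the month 6 values themselves contribute about 0.01 to 0.04 of that.

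**The case against.** The strongest reply is that the planned test is legitimate. It is unbiased under randomisation and belongs to an aim that the protocol calls exploratory in spirit. The metabolomic paragraph can also be read as a specific rule that overrides the general one. This stands, and it limits the point to efficiency and clarity. It does not remove the gain, and one clause would settle which rule governs.

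Several stronger readings are tempting, but the documents do not support them:

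- *Precision is lost by departing from the mixed model set for all study endpoints.* That model has no baseline covariate, and with complete data it gives the same month 12 variance as the t-test. The gain comes from baseline adjustment, which section 9.1 does not specify for any treatment comparison.
- *Baseline is thrown away, or the analysis is on raw values.* Baseline is subtracted, and the transformation rule covers all endpoints. What is missing is adjustment.
- *Month 6 metabolite data are wasted.* No section commits to assaying month 6 samples for metabolomics, and section 3 describes them differently from the baseline and final samples. Using them might require a third set of assays, and their contribution is small.
- *This is the least powered comparison in the trial.* The figure of 39 per group is for NAF only. The tissue subgroup, with 50% consent expected in section 2.3.4, could be smaller: 60 × 0.5 = 30 per group.

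**Conclusion.** The point holds as one of efficiency. The planned t-test on change is valid but less precise than baseline adjustment. With equal variances, adjustment cuts the variance by 35% at r = 0.3, 25% at 0.5, 15% at 0.7 and 5% at 0.9. The size rests on r, which the documents do not report and which will differ between metabolites. For very stable compounds the gain is slight. The proportional gain does not depend on sample size, so it applies to NAF and plasma alike.

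A smaller matter of wording goes with it: the general rule and the metabolomic rule in section 9.1 name different methods, and the plan does not say which governs. Nothing here implies bias or an error in the sample size figures. The change is worth making because it is free, not because the planned analysis is unsound.

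**What to change.** In the metabolomic paragraph of section 9.1:

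1. For each metabolite, transformed where the section's normality rule calls for it, replace the two-sample t-test on change with an ANCOVA of the month 12 value on arm and the baseline value. Pass the arm p-values to the existing q-value step unchanged.
2. State that post-intervention means month 12, and that the metabolomic aim is an exception to the mixed model for all study endpoints.
3. State whether month 6 NAF and plasma are to be assayed for metabolomics. Only if they already are, a baseline-adjusted longitudinal model with the month 12 arm contrast may be used instead. Expect little from it beyond some recovery when women are missing at month 12.

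Items 1 and 2 cost a change of wording and a scripted model per metabolite, settled before unblinding. They need no new participants, samples or assays. Item 3 is also wording only, unless the sponsor chooses to add month 6 assays, and the gain shown here does not justify that on its own.
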